Normal controls will be included to adjust for the baseline impact of HMD on visual fields and gait parameters and to compare these to data from patients with RP. Comparing to a group of age-matched control patients will allow us to investigate and understand the true impact of HMD on visual fields, gait, and quality of life. Control participants will be recruited from the Comprehensive and Pediatric Ophthalmology Services at the University of Michigan. We will seek to enroll up to 40 subjects in order to obtain ten patients and ten age-matched controls with complete data, allowing room for those who don't complete both study visits and technical errors with equipment.

Criteria

Inclusion criteria for subjects with retinal dystrophy:

- diagnosis of retinal dystrophy
- severe vision loss that constitutes legal blindness
- able to perform a reliable Goldmann visual field test
- constricted visual field less than or equal to 20 degrees by Goldmann perimetry using the III4e stimulus in at least one eye with best-corrected visual acuity $\geq 20/60$

Inclusion criteria for control subjects:

- healthy controls
- able to perform a reliable Goldmann visual field test

Exclusion criteria for subjects with retinal dystrophy:

- movement disorder that precludes evaluation of mobility
- functional vision loss
- pregnant women

Exclusion criteria for control subjects:

- visually significant ocular condition other than correctable refractive error
- movement disorder that precludes evaluation of mobility
- functional vision loss
- pregnant women

c. Study Setting

Patients will be recruited from the Retinal Dystrophy Clinic of the Department of Ophthalmology and Visual Sciences at the University of Michigan; controls will be recruited from the Comprehensive and Pediatric Clinics of the Department of Ophthalmology and Visual Sciences at the University of Michigan. Study exams, clinical testing, surveys and interviews will be completed in the Kellogg Clinical Research Center. Mobility testing will be conducted in a hallway located in the Kellogg Clinical Research Center.

d. Outcome measures

Primary Outcome Measures:

- Change in the planimetric area of Goldmann visual field with the use of head-mounted display technology compared to baseline (measured in degrees squared):
Using computer software we will calculate the area of participants' Goldmann visual fields in order to obtain a summary quantitative measurement of the extent of peripheral vision.

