To address Aim 2 we will measure change in gait speed with and without the use of OHMD. We will calculate percent preferred walking speed to compare the ratio of gait speed measured in the presence and absence of physical obstacles. We will also use our data processing algorithms to reconstruct the paths of the feet and head movements during the planned experiments from which we can estimate mobility parameters (9–11). For gait, we will gather measures of stride length, width and period, and their variabilities, from straight-line walking, lateral/foot-angle relation, stride frequency, ground contact time, etc. For head movement we will gather measures of head pitch, head roll and head yaw. The mean and standard deviation of each gait and head movement parameter will be compared before and after being trained to use optical head-mounted display technology (11,12). We will use Wilcoxon signed-rank test to test for significant differences. Significant changes (and trends) will be assessed for direction and magnitude, and resulting values will be compared to gait and head movement parameter norms before and after using the optical head mounted display. The Mann-Whitney U test will be used to compare changes in gait parameters between patients and controls.

To address Aim 3 we will use the Wilcoxon signed-rank test to determine whether individual participants' survey scores changed from baseline when using optical head mounted display technology. We will also use the Mann Whitney U test to compare changes in survey scores between patients and controls. Cohen's d will be calculated to measure the overall effect size of the intervention as measured by the surveys. Minimum clinically important differences will also be calculated (ratio of change in visual ability to 1.95 standard errors of the measured change) to determine if changes in each individual's visual ability were clinically important.

We will also calculate Spearman correlations between variables (visual field area, mobility parameters and survey results) and use multiple regression to investigate associations while controlling for covariates.

Image 1. The Epson Moverio® Head Mounted Display.

Image 2. The Actigraph Link Inertial Motion Unit.

References

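### Aim 2 ties the size of within-patient gait and head changes to significance or an undefined trend, across roughly 20 to 39 uncorrected tests on about ten patients, so selected estimates may be inflated

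*Combined protocol and SAP*

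**What the plan says.** The Aim 2 paragraph of Planned Data Analysis (section e) starts with gait speed and percent preferred walking speed. It then names the gait measures "stride length, width and period, and their variabilities, from straight-line walking, lateral/foot-angle relation, stride frequency, ground contact time, etc" and three head measures: pitch, roll and yaw. The mean and the SD of each are compared before and after training. The test is given as "We will use Wilcoxon signed-rank test to test for significant differences", and the next sentence begins "Significant changes (and trends) will be assessed for direction and magnitude", with a comparison to norms to follow.

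The section does not state an alpha or sidedness, define a trend, close the list of parameters, adjust for the number of tests or plan an interval estimate. Eligibility (section b) allows up to 40 enrolled subjects "in order to obtain ten patients and ten age-matched controls with complete data".

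Two other places matter. Outcome measures (section d) lists change in gait speed as secondary, and changes in stride length, stride width and foot orientation as other outcomes, none with a significance condition. The Aim 2 paragraph also ends with a Mann-Whitney comparison of gait changes between patients and controls, which is not restricted to significant parameters.

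**The concern.** When magnitude is looked at after a significance filter, the estimates that pass are those that happened to be large. With about ten pairs, a small or moderate true change can pass only if the sample overstates it, so the selected estimates are biased upward. The more parameters are screened, the more chance results pass as well. Adding trends without a definition lets more chance results through and leaves the threshold to be chosen after the data are seen.

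The measures also overlap. Stride period and stride frequency are reciprocals, and speed is stride length times stride frequency, so one change in walking can appear under several names and look like independent confirmation.

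At stake is what the pilot contributes on mobility. Its most useful product under Aim 2 is an unselected estimate, with its uncertainty, for each parameter. For stride period and frequency, contact time, head pitch, roll and yaw, and all the SDs, the plan promises no within-patient estimate outside the filtered sentence. By contrast, the Aim 3 paragraph plans Cohen's d for the surveys with no significance condition.

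**Working it through.** The documents give no alpha, power, effect size or test count, so there is no planned figure to reproduce.

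**Number of tests (from Planned Data Analysis and Study Design)**

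- Gait parameters named: stride length, width, period, foot-angle relation, frequency and contact time = 6. Head parameters: 3.
- Mean and SD of each: (6 + 3) × 2 = 18.
- Add gait speed and percent preferred walking speed: 18 + 2 = 20 for one walk.
- Study Design has an empty and an obstacle walk. If each summary were tested on both: 18 × 2 + 2 (speed on each walk) + 1 (percent preferred walking speed, which already combines the walks) = 39. This is rounded to 40 below.
- The device-off and device-on walks at follow-up could raise the count. They are not included.

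**Assumptions.** Ten pairs, two-sided tests, 5% for significant, p ≤ 0.10 for a trend, normally distributed changes, no ties.

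**Exact size of the test.** Ten pairs give 2^10 = 1,024 sign patterns. Of these, 50 have p ≤ 0.05 (50/1,024 = 0.0488) and 86 have p ≤ 0.10 (86/1,024 = 0.0840).

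**Chance findings if nothing changes**

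- Expected number at 5%: 20 × 0.0488 = 0.98; 40 × 0.0488 = 1.95.
- Expected number with trends: 20 × 0.0840 = 1.68; 40 × 0.0840 = 3.36.
- Chance of at least one at 5%, independent tests: 1 − (1 − 0.0488)^20 = 63%; 1 − (1 − 0.0488)^40 = 86%.
- The tests are correlated, which lowers this. By simulation it is about 45% and 61% at a between-test correlation of 0.5, and about 33% and 43% at 0.7.

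**Inflation of selected estimates.** The ratio is the mean absolute estimated change among results that pass the filter, divided by the true change (300,000 simulated trials for each true value, in SD units of the paired change).

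| True standardised change | Power at 5% | Ratio, p ≤ 0.05 | Ratio, p ≤ 0.10 |
|---|---|---|---|
| 0.3 | 13% | 2.5 | 2.3 |
| 0.5 | 28% | 1.7 | 1.6 |
| 0.8 | 60% | 1.2 | 1.2 |
| 1.0 | 79% | 1.1 | 1.1 |

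The looser filter admits more chance findings but inflates slightly less. With no filter the ratio is 1.00.

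**The case against.** A reader might infer that only significant parameters will be reported. The text does not say so. It compares every parameter before and after, lists four gait outcomes with no significance condition, and leaves the between-group gait comparison unfiltered. This part of the objection stands, and it confines the problem mainly to the parameters and SDs outside the outcome list. It does not remove it: the outcome list gives no analysis rule of its own, the Mann-Whitney comparison has no planned estimate and names gait but not head parameters, and the only within-patient statement on magnitude is the conditional one.

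A reader might also infer that the reported effects will be overstated two- to threefold or be pure chance. That does not follow. The documents give no true effect, the inflation nearly disappears for large changes, and a head-mounted display could alter gait a lot or a little.

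The upper count is also open to challenge. The plan does not say that every summary is tested on both walks, and it ties at least some stride measures to straight-line walking. The overlap between measures argues against the independent-test percentages, which is why a range is given.

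Finally, this is a pilot and Aim 2 sits under Other Aims. That excuses low power and lowers the weight of the point, but it is no reason to estimate effects selectively.

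**Conclusion.** The concern holds in a limited form. The plan states a rule, and following it gives upward-biased within-patient estimates for whichever gait and head parameters pass. Under the assumptions above, the inflation runs from about 2.5 times at a true standardised change of 0.3 to 1.1 times at 1.0. It would be smaller if more than ten patients had complete data.

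If the device changes nothing, about 1 to 2 chance findings are expected at 5%, or 1.7 to 3.4 if trends mean p ≤ 0.10. The chance of at least one at 5% is about 33% to 63% for 20 tests and 43% to 86% for 40, for between-test correlations from 0.7 down to 0. A chance finding is therefore plausible or likely, not certain.

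The point does not touch the primary aim. It is a correction of wording that should be made, because it decides which mobility estimates the pilot yields.

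**What to change.** Replace the sentence on significant changes and trends with: *For every gait and head movement parameter analysed we will report the median (Hodges-Lehmann) change with its 95% CI, whatever the p-value.* Delete the reference to trends, and label all parameters other than the four in the outcome list as exploratory.

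A multiplicity correction is not a substitute at this size. The smallest two-sided p with ten pairs is 2/1,024 = 0.00195, which exceeds 0.05/26 = 0.00192, so with 26 or more tests nothing could pass Bonferroni. A lone result at that minimum among 40 tests would have a Benjamini-Hochberg value of 40 × 0.00195 = 0.078.

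Restricting Aim 2 to a single gait test, closing the parameter list, or keeping only one of stride period and stride frequency are reasonable options, but they are matters of preference and the fix does not depend on them.

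The cost is a change of wording, a longer results table and fewer parameters that can be called findings. No data collection changes. The intervals will be wide: a 95% t-interval on ten pairs has a half-width of about 2.262/√10 = 0.72 SD of the change, which shows the reader how little ten patients can settle.

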- Impact of Vision Impairment Questionnaire (4) and Independent Mobility Questionnaire (6)
- Mobility testing, as detailed in below (Aim 2)

Participants will be fit with HMD technology (Epson Moverio www.epson.com/moverio; **Figure 2**) and undergo a brief training with the investigators to learn about use of the device and will receive materials describing how to charge the device and turn it on and off. While wearing the device the subjects may have some discomfort related to the weight of the device on the ears and/or nose. The nose piece can be adjusted with pads for optimal comfort. A band on the arm pieces of the frame can also be adjusted for comfort. Initially, there may be the sense of disorientation, may feel dizzy or nausea, but with coaching/training the subject is anticipated to adapt. In order to adapt to the technology, participants will be permitted to bring the HMD home to use (for 2-4 weeks).

When participants return after a period of adaptation to the HMD, they will undergo the following:

- Impact of Vision Impairment Questionnaire (4), Independent Mobility Questionnaire (6), and the System Usability Scale (12)
- Videotaped open-ended interview in which subjects will be asked to describe their experience using HMD and to discuss any challenges and successes using the technology.
- Goldmann visual field and tablet visual field examination (while wearing the HMD)
- Mobility testing, as detailed below (Aim 2; while wearing the HMD)

To accomplish Aim 1 we will use the following approaches:

After the period of in-home adaptation, participants will return to have their visual field retested with Goldmann perimetry after a period of adaptation to the technology. We predict the outcome of increased planimetric area of the peripheral vision determined by Goldmann perimetry.

To accomplish Aim 2:

We propose to collect and analyze gait and head movement parameters in order to provide a quantitative analysis of mobility-associated factors of persons with severe visual field constriction and controls with and without the use of optical head-mounted display technology. We will mount an inertial measurement unit (IMU) data logger (Actigraph GT9X "Link", <http://www.actigraphcorp.com/products/actigraph-link/>; **Image 2**) on the patients' shoe; it will be placed inside a small pouch that rests on top of the shoe laces. A second IMU device will be mounted on

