the frames of the patients' existing glasses (or on a mock frame if the patient does not wear glasses) in order to measure head pitch, roll and yaw. The subjects will be asked to walk around a long empty corridor during which time they will be timed and videotaped and IMU data will be acquired. Then, participants will be asked to walk the same corridor after obstacles are arranged in the corridor every 1-2 meters. Obstacles will be short pieces of foam lying on the floor, knee to waist high cardboard boxes, or pieces of foam hanging from the ceiling. A research assistant will follow close to participants in order to provide assistance should this be required. Testing mobility in the presence of obstacles is important in order to more closely approximate real-world scenarios. Video recording is essential in order to correlate aberrancies in IMU data with obstacles in the patients' environment. The same procedure will be repeated with the patients wearing optical head-mounted display technology after the period of in-home adaptation to the technology with the device turned off (to serve as a negative control) and with the device turned on.

To accomplish Aim 3:

Participants will all complete the Impact of Vision Impairment and Independent Mobility Questionnaire at the time of their enrollment in the study. These surveys will be completed again after the period of in-home adaptation to the OHMD. We will also analyze qualitative data collected through open-ended interviews after use of HMD.

We will conduct statistical analyses, as detailed in Section 2e, to describe associations between outcomes assessed throughout our Aims.

b. Eligibility

Participants with retinal dystrophy will be recruited into this study from the Retinal Dystrophy Clinic in the Department of Ophthalmology and Visual Sciences at the University of Michigan.

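### Aim 2 plans a patient–control test of change for gait but not for head movement, and the device-off walk that would separate wearing from display effects has no stated place in the analysis

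*Combined protocol and SAP*

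**What the plan says.** **Study Design, Aim 2 text.** The aim's scope is stated as "We propose to collect and analyze gait and head movement parameters" for "persons with severe visual field constriction and controls with and without the use of optical head-mounted display technology". A second motion sensor is mounted on the participant's own glasses, or on a mock frame, "in order to measure head pitch, roll and yaw". After the home adaptation period the corridor and obstacle walks are repeated "with the device turned off (to serve as a negative control) and with the device turned on".

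**Planned Data Analysis, Aim 2 paragraph.** Each gait and head movement parameter is compared before and after training, with the Wilcoxon signed-rank test. Then "resulting values will be compared to gait and head movement parameter norms before and after using the optical head mounted display". The paragraph ends: "The Mann-Whitney U test will be used to compare changes in gait parameters between patients and controls". It gives no source for the norms and no significance level, and it does not mention the device-off walk.

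**Eligibility.** The reason for recruiting controls begins: "Normal controls will be included to adjust for the baseline impact of HMD on visual fields and gait parameters". The next sentence adds quality of life. The target is ten patients and ten age-matched controls with complete data, from up to 40 enrolled.

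**Outcome measures.** Gait speed is the secondary outcome. Stride length, stride width and foot orientation are among the other outcomes. Head movement is not listed.

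**The concern.** The aim and its analysis differ in scope. Head movement is measured in both groups, yet the only Aim 2 test that sets patients against controls names gait alone.

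Head motion is also directly exposed to having a headset on. Study Design itself warns of weight on the ears and nose, and of early disorientation, dizziness or nausea. At baseline the head sensor sits on ordinary or mock frames. At follow-up the participant wears the display and has walked the corridor before. A change in head pitch or yaw in patients could therefore come from the display, from wearing it, or from repeating the course, and the planned before/after test cannot tell these apart. What is at stake is whether a head-movement finding can be attributed to the display, or to field loss, rather than to wearing a headset.

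**Working it through.** The plan gives no power, significance level, SD or effect size for Aim 2, so there is no figure to reproduce. The check is a comparison of the text, followed by an illustration under assumed inputs.

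**1. Coverage of the planned comparisons (Planned Data Analysis)**

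| Domain | Within-person test | Patient–control test of change | Device on versus off |
|---|---|---|---|
| Visual field area | change analysed, no test named | Mann-Whitney | no off condition described |
| Gait | signed-rank | Mann-Whitney | walks collected, contrast not stated |
| Head movement | signed-rank | **none** | walks collected, contrast not stated |
| Survey scores | signed-rank | Mann-Whitney | not applicable |

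Head movement is the only one of the four without a between-group test. Gait is probably not shorthand for both: the same paragraph lists gait measures and head measures separately, and twice names the two together before the Mann-Whitney sentence names gait only.

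**2. What each contrast estimates**

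Write a person's change as D (display) + W (wearing) + R (repeating the course), with subscript p for patients and c for controls.

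- Before/after in patients: D_p + W_p + R_p.
- Device on minus device off in patients, at the same visit: D_p, apart from any effect of the order of the two walks.
- Patients minus controls on change: (D_p − D_c) + (W_p − W_c) + (R_p − R_c). If wearing and repetition act alike in both groups, this is D_p − D_c, the patient-specific part.

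The plan commits only to the first for head movement. The second and third answer different questions, and neither replaces the other.

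**3. Illustration (assumed inputs)**

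Ten patients and ten controls (Eligibility). Assumed: normal changes with SD 1, two-sided 5%, no display effect, and the same wearing effect w in both groups. The table gives the share of simulated trials with p < 0.05.

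| w (SD of change) | Patients, before/after signed-rank | Patient–control Mann-Whitney | Runs |
|---|---|---|---|
| 0 | 4.5% | 3.8% | 4,000 |
| 0.25 | 10.5% | 3.9% | 6,000 |
| 0.5 | 27.6% | 4.0% | 4,000 |
| 0.75 | 54.6% | 4.5% | 6,000 |
| 1.0 | 78.7% | 4.1% | 4,000 |

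A device-on versus device-off signed-rank test stayed at about 5% (4.7%, 4.5% and 5.3% at w = 0, 0.5 and 1.0). That follows by construction, because wearing is present in both walks and cancels.

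**4. Precision of the between-group test**

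The difference detectable with 80% power at 10 versus 10 is √(2/10) × (1.960 + 0.842) = 0.447 × 2.802 = 1.25 SD for a comparison of means. Dividing by √(3/π) = 0.977, for the large-sample efficiency of the rank test under normality, gives 1.28 SD. These are large-sample approximations; at ten per group the true requirement is somewhat higher.

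**The case against.** The strongest reply is that the design already has a control for wearing: the device-off walk, made by the same person with the headset on. This stands. A reader might infer that the effect of wearing a headset will be read as a display effect. The documents do not support that, because the data that separate the two are collected for that purpose. What remains is that the analysis section never assigns this walk to a comparison. Its one near-reference, to gait speed with and without the display, does not say whether *without* means baseline or device off, and it does not cover head movement.

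A second reply is that the patient–control contrast is weak at this sample size, and removes wearing only if wearing acts alike in both groups. Both points are right. That is why the between-group test should support only claims specific to patients, with on versus off supporting claims about the display. Running separate before/after tests in each group would not replace a comparison between groups.

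Third, Aim 2 puts controls within its scope but prescribes no between-group test for head movement. Nor can it be inferred that Eligibility restricts controls to visual fields and gait, since quality of life follows. The argument rests on the mismatch of scope, not on a broken commitment.

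Fourth, a reader might infer that obstacle-course values are to be judged against norms for unobstructed walking, with a measurable bias. The plan does not say so. Stride measures come from straight-line walking, and obstacles enter through a ratio of speeds with and without them. No size can be put on such a bias; only the missing source of the norms stands.

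Finally, head movement is not a listed outcome and this is a pilot. That limits the stakes, but the correction costs very little.

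**Conclusion.** The point holds in limited form. Aim 2 spans gait and head movement in both groups, but the planned between-group test covers gait only, and the head-movement test that remains cannot separate display, wearing and repetition. Because the device-off walk exists but has no analysis role, misattribution is possible and avoidable, not inevitable.

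The illustrated size, about 28% significant results at a shared wearing effect of 0.5 SD and 79% at 1.0 SD, depends wholly on assumptions: ten per group, normal changes, two-sided 5%, no display effect, and equal wearing effects in the two groups. The documents give no basis for the size of any wearing effect. The figures show what the before/after test can do, not what it will do here.

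The primary outcome is unaffected. This is a worthwhile, inexpensive improvement to an exploratory analysis.

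**What to change.** In the Aim 2 paragraph of the Planned Data Analysis:

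1. Extend the Mann-Whitney sentence so that it covers changes in both gait and head movement parameters between patients and controls. Base any claim of a patient-specific head-movement effect on that comparison.
2. Add a within-person signed-rank comparison of the device-on with the device-off walk, for gait and head movement. Base any claim of a display effect, as distinct from a wearing effect, on it.
3. Make this trial's controls, walking the same corridor in the same obstacle condition, the main reference for levels. Keep published norms, if used, as description, and cite their source.

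The sentence on repeat walks in the Aim 2 text refers to patients, while the list of return-visit procedures refers to participants. Confirm that controls also make the follow-up walks, since items 1 and 3 rely on control data.

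**Cost.** A few sentences and some extra exploratory comparisons, with no new participants, visits or procedures if controls follow the return-visit list. The between-group test is imprecise (80% power only at about 1.25 to 1.28 SD), so a non-significant result should not be read as no patient-specific effect. Ten controls may also be a less precise reference for levels than a large published norm.

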Secondary Outcome Measures:

- Change in gait speed compared to baseline (measured in seconds):
Gait speed will be measured using an inertial measurement unit attached to participants' shoes and will quantify the time taken to move from the beginning to end of a short mobility course.

Other Outcome Measures:

- Change in patient-reported ability for independent mobility as assessed by subject responses a validated questionnaire:
Independent Mobility Questionnaire (scored from 35 to 175 with 175 representing extreme mobility impairment)
- Change in patient-reported mobility and independence as assessed by subject responses a validated questionnaire:
Mobility and Independence domain of the Impact of Vision Impairment Questionnaire (scored from 0 to 33 with 0 representing poor mobility and independence)
- Change in stride length compared to baseline (measured in mm):

Inertial measurement units attached to participants' shoes will track the length of each step as they walk through a short mobility course.

- Change in stride width compared to baseline (measured in mm):
Inertial measurement units attached to participants' shoes will track the width of each step as they walk through a short mobility course.
- Change in foot orientation compared to baseline (measured in degrees):
Inertial measurement units attached to participants' shoes will track the orientation of their feet as they walk through a short mobility course.

e. Planned Data Analysis

To address Aim 1 the visual field will be assessed before and after being trained to use optical head-mounted display technology. The Goldmann visual field plots will be scanned and the planimetric areas for each stimulus size will be measured using Adobe Photoshop CC (San Jose, CA) as previously described (8). In brief, using a scale of 10 degrees on the visual field, the corresponding number of pixels are determined, and the units are set to millimeters. Areas are measured in mm² using the Magic Wand tool and are converted to degrees squared. Areas of scotomas are subtracted from the total area. We will analyze the change in area before and after a 2-4 week period of adaptation to the OHMD. The adaptation period is important as it will allow subjects to become familiar with how to use the device and to gain insight into how using such a device may impact their life. The Mann-Whitney U test will be used to compare change in visual field area between patients and controls.

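### Cohen's d for the surveys is planned on about ten patients and ten controls with no small-sample correction and no confidence interval

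*Combined protocol and SAP*

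**What the plan says.** The Aim 3 paragraph of section e (Planned Data Analysis) plans three things for the surveys before it turns to individual-level change:

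- a Wilcoxon signed-rank test of whether participants' "survey scores changed from baseline when using optical head mounted display technology";
- a Mann-Whitney U test to "compare changes in survey scores between patients and controls";
- Cohen's d, which "will be calculated to measure the overall effect size of the intervention as measured by the surveys".

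Nothing more is said about d. No group, denominator SD, small-sample correction, interval or sign convention is given.

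The sample size is in section b (Eligibility): "We will seek to enroll up to 40 subjects in order to obtain ten patients and ten age-matched controls with complete data". Both groups fill in the surveys: "Participants will all complete the Impact of Vision Impairment and Independent Mobility Questionnaire at the time of their enrollment in the study".

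Section d (Outcome measures) scores the two surveys in opposite directions. The Independent Mobility Questionnaire is "scored from 35 to 175 with 175 representing extreme mobility impairment". The Mobility and Independence domain of the Impact of Vision Impairment Questionnaire is "scored from 0 to 33 with 0 representing poor mobility and independence".

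**The concern.** Cohen's d divides a mean by an SD estimated from the same small sample. The reciprocal of an estimated SD is on average larger than the reciprocal of the true SD, so d overstates the true standardised effect. The bias fades as the sample grows, but at ten per group it is a visible percentage. A simple correction exists, and the plan does not mention it.

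The missing interval matters more. A bare d from ten patients looks precise and is not. A reader given one number per survey cannot see that the data may be compatible with no effect or with a very large one.

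The sign also needs a convention. A patient who improves moves down on one questionnaire and up on the other, so the same benefit gives a negative d on one and a positive d on the other.

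What is at stake is how the survey results of this pilot are described. The surveys are listed under Other Outcome Measures, and no planned test uses d.

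**Working it through.** The plan states no effect size, SD or power figure, so there is no figure of its own to reproduce. The check asks how large the bias is under each reading that the text allows.

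**Inputs.** Ten patients and ten controls with complete data (section b). Because the text does not fix the form of d, the degrees of freedom are 9 within patients, 18 between groups, or 19 for change over all 20 participants. Normally distributed changes are an assumption of this check; the documents do not state it.

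**Formula.** The exact small-sample factor is J(df) = Γ(df/2) / [√(df/2) × Γ((df − 1)/2)]. The mean overstatement of uncorrected d is 1/J − 1, and Hedges' g = J × d.

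**Results.**

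- Within ten patients, SD of change or baseline SD: J(9) = Γ(4.5) / [√4.5 × Γ(4)] = 0.914, and 1/0.9139 − 1 = 9.4%.
- Between two groups of ten: J(18) = 0.958, so 4.4%.
- All 20 participants together: J(19) = 0.960, so 4.2%.
- Within ten patients, average of the two visits' SDs: about 4.7% to 7.4% by simulation, for assumed between-visit correlations of 0.3 to 0.8.

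A simulation of 400,000 normal samples of ten agrees with the first line: a true d of 0.50 gave a mean uncorrected d of 0.547.

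**Other numbers of completers.** Up to 40 may be enrolled, so the number of complete patients could differ from ten. For the first reading the overstatement is 12.6% at n = 8, 7.5% at n = 12, 5.8% at n = 15 and 4.2% at n = 20.

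**Sampling error.** Take an observed within-patient d of 0.50 with n = 10, standardised by the SD of change. Then t = 0.50 × √10 = 1.58 on 9 degrees of freedom. Inverting the noncentral t distribution gives a 95% confidence interval for the true d of about −0.17 to 1.15. In the simulation at a true d of 0.50, the observed d had an SD of about 0.39, against a mean bias of 0.547 − 0.50 = 0.047, about 0.05.

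**After the fix.** An observed d of 0.50 becomes g = 0.914 × 0.50 = 0.46 within patients, or 0.958 × 0.50 = 0.48 between groups.

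**Direction (illustrative).** An improvement of 0.5 SD on both surveys gives −0.5 on the Independent Mobility Questionnaire and +0.5 on the other if raw scores are used. Once aligned, both are +0.5.

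**The case against.** The strongest objection is that the bias hardly matters. It is about 0.05 on an estimate whose SD is about 0.39, it touches neither the primary outcome nor the rank tests, and any reader who knows n and the form of d can apply the factor afterwards. The factor is also exact only under normality, whereas these are bounded questionnaire scores that the plan itself analyses by ranks. All of this stands, and it is why the point is minor. It does not remove the case for a correction that costs nothing, and it strengthens the case for an interval.

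A reader might infer more than the documents support, in four ways:

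- *That the bias is 9%.* The plan does not fix a within-patient d. The sentence just before it compares patients with controls, and a between-group d gives about 4%.
- *That one d will be averaged over both surveys, so that opposite signs cancel.* The text does not say this. The next sentence turns to each individual's change, so the word overall reads more naturally as group-level. The sign convention is still needed with one d per survey.
- *That dividing by the SD of change inflates d further.* With equal SDs at both visits, the ratio to the baseline-SD version is 1/√(2(1 − r)), where r is the between-visit correlation. It is above 1 only when r exceeds 0.5: 1.29 at r = 0.7, 1.00 at 0.5 and 0.85 at 0.3. The documents give no r. The two versions are also different quantities; neither is a biased form of the other.
- *That a later trial would be undersized by about 16%* (1 − 0.9139² = 16.5%). The documents mention no follow-on trial sized on d, and the figure takes the within-patient reading as given.

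**Conclusion.** The point holds as a minor, free improvement. As written, the plan would report a d that is on average about 4% to 9% too large, depending on which d is meant, and would report it without an interval. The range assumes normal changes, ten complete participants per group and no correction beyond what the text names. The bias is small beside the sampling error at this sample size, so the interval is the more useful half of the change. The primary outcome, the Wilcoxon and Mann-Whitney tests and the individual-level calculation of important change are unaffected. Nothing here supports a claim that the survey conclusions would be wrong.

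**What to change.** Replace the Cohen's d sentence in the Aim 3 paragraph of section e with one that specifies:

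- Hedges' g, that is, the chosen d multiplied by the exact small-sample factor for its degrees of freedom (0.914 for 9, 0.958 for 18);
- one g for each survey that has a baseline score. The System Usability Scale is given only at the return visit, so it has no change score;
- the group (within patients, or patients against controls) and the SD in the denominator, both chosen before the data are seen;
- a sign such that positive means improvement on both surveys, which means reversing the Independent Mobility Questionnaire;
- a 95% confidence interval and its method. The noncentral t distribution serves for a d based on the SD of change or for a between-group d. If the baseline SD is chosen, the interval also depends on the between-visit correlation, so a method that allows for it, such as a bootstrap over participants, should be named.

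The cost is a sentence or two of wording. No new data are needed and no planned test changes. The reported effect becomes slightly smaller, by about 9% within patients (1 − 0.914 = 8.6%) or 4% between groups (1 − 0.958 = 4.2%).
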